Patients who test positive for a past or active Hepatitis B infection should be given prophylactic administration. If the patient has a positive Hepatitis B test result, they should be treated with Hepatitis B anti-viral lamivudine 100 mg prior to start of RAD001 therapy and throughout the treatment period with RAD001. Some associated toxicities to the lamivudine may include headache, diarrhea, and rash. If the patient needs to be treated with lamivudine, the cost of the treatment will be charged to the patient's insurance. For guidance on management of Hepatitis B and C reactivation, refer to Section 3.2.6.4.

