3.2.6.4 Management of Hepatitis B or C Reactivation

Monitoring and prophylactic treatment for hepatitis B reactivation

Table 3-2 provides details of monitoring and prophylactic therapy according to the baseline results of viral load and serologic markers testing.

Table 3-2 Action to be taken for positive baseline hepatitis B results

Test	Result	Result	Result	Result	Result
HBV-DNA	+	+ or -	-	-	-
HBsAg	+ or -	+	-	-	-
HBs Ab	+ or -	+ or -	+	+ or -	- or + with prior HBV vaccination
HBc Ab	+ or -	+ or -	+ or -	+	-
Recommendation	Prophylaxis treatment should be started 1-2 weeks prior to first dose of study drug Monitor HBV-DNA approximately every 6 weeks		No prophylaxis Monitor HBV-DNA approximately every 3 weeks		No specific action

Antiviral prophylaxis therapy should continue for at least 4 weeks after last dose of study drug. For patients who have already received study drug prior to the approval of the amendment, the same process should be followed at the patient's next visit. The first HBV-DNA result would be regarded as baseline. For hepatitis B reactivation, definition and management guidelines, see Table 3-3 Guidelines for management of hepatitis B.

Table 3-3 Guidelines for management of hepatitis B

HBV reactivation (with or without clinical signs and symptoms)*	
For patients with baseline results: Positive HBV-DNA OR positive HBsAg ----- reactivation is defined as: [Increase of 1 log in HBV-DNA relative to baseline HBV-DNA value OR new appearance of measurable HBV-DNA]	Treat: Start a second antiviral AND Interrupt study drug administration until resolution: ≤ baseline HBV-DNA levels If resolution occurs within ≤ 28 days, study drug should be re-started at one dose lower, if available. If the patient is already receiving the lowest dose of study drug according to the protocol, the patient should restart at the same dose after resolution. Both antiviral therapies should continue at least 4 weeks after last dose of study drug. If resolution occurs > 28 days, patients should discontinue study drug but continue both antiviral therapies at least 4 weeks after last dose of study drug.

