- ³All patients should be screened for hepatitis risk factors and any past illnesses of hepatitis B and hepatitis C infection. It is highly recommended that patients positive HBV-DNA or HBsAg are treated prophylactically with an antiviral (i.e. Lamivudine) for 1-2 weeks prior to receiving study drug (see Section 3.2.6.4). The antiviral treatment should continue throughout the entire study period and for at least 4 weeks after the last dose of everolimus. Patients on antiviral prophylaxis treatment or positive HBV antibodies should be tested for HBV-DNA on Cycle 1 Day 1 and Day 1 of all subsequent cycles (every 28 days) to monitor for re-activation. If re-activation is confirmed, everolimus must be interrupted or discontinued according to the guidance in Table 3-3. Patients with viral hepatitis C risk factors should be screened for HCV RNA-PCR. Patients with positive HCV RNA-PCR results at screening and/or a history of past infection (even if test at baseline is negative) will be ineligible for the study.
- ⁴**Thyroglobulin and thyroA are both drawn at monthly visits only if AT BASELINE thyroA lab value is negative AND thyroglobulin value is elevated.**
- ⁵CT/MRI scans are to be performed every 2 months until first progression or death through 24 months from study entry. Post 24 months, if a patient has already stopped study treatment, but still alive without first progression, follow for first progression (CT/MRI scans every 3 months) and survival through 5 years from study entry. Post 24 months, If patient is scheduled to continue treatment, follow for first progression (CT/MRI scans every 3 months) and survival through 5 years from study entry; If treatment is stopped post 24 months but prior to 5 years from study entry for reasons other than progression, follow for first progression and survival through 5 years from study entry; if treatment is stopped post 24 months but prior to 5 years from study entry due to first progression, follow until death or 5 years from study entry, whichever is first.;

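### Section 3.2.5j gives lamivudine for past hepatitis B infection where Table 3-2 withholds it, and Tables 3-1 and 3-3 disagree on RAD001 after a life-threatening reactivation

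*Combined protocol and SAP*

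**What the plan says.** Three places in the protocol govern antiviral prophylaxis.

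- Section 3.2.5j: "Patients who test positive for a past or active Hepatitis B infection should be given prophylactic administration". The next sentence names the drug, to be given before and throughout RAD001: "If the patient has a positive Hepatitis B test result, they should be treated with Hepatitis B anti-viral lamivudine 100 mg".
- Table 3-2 in section 3.2.6.4 sorts patients by HBV-DNA, HBsAg, HBs Ab and HBc Ab. Patients positive for HBV-DNA or HBsAg receive prophylaxis. Those negative for both but antibody positive have the entry "No prophylaxis Monitor HBV-DNA approximately every 3 weeks".
- Footnote 3 of Table 3.4a (section 3.4.1): "It is highly recommended that patients positive HBV-DNA or HBsAg are treated prophylactically with an antiviral". It recommends prophylaxis for no other group.

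Three places govern stopping or restarting RAD001.

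- Table 3-3, for hepatitis B reactivation: "If resolution occurs within ≤ 28 days, study drug should be re-started at one dose lower, if available". A patient already on the lowest dose restarts at that dose. RAD001 stops only if resolution takes more than 28 days. The table's footnote records reactivation as grade 3, or as grade 4 if the investigator judges it life threatening.
- Table 3-1, for toxicity in general: grade 4 non-hematological toxicity means discontinuation, with hyperlipidemia the only exception. So does any toxicity that needs an interruption of three weeks or more.
- Section 3.2.4: a dose delay of more than 21 days requires discontinuation from the study. No exception is given.

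**The concern.** A site following the protocol as written can reach opposite decisions for one patient, depending on which section it opens. Both decisions bear on safety. Section 3.2.5j itself says antivirals lower the risk of reactivation and of the illness and death that go with it, so wrongly withholding lamivudine matters. Giving it without need exposes the patient to a drug about which the protocol says: "Some associated toxicities to the lamivudine may include headache, diarrhea, and rash". The cost goes to the patient's insurance. Whether to give RAD001 again after a life-threatening reactivation is the more serious decision, and the two tables answer it differently. Institutions outside the lead center also treat patients, so different readings at different sites are realistic.

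**Working it through.** The plan states no figure to reproduce here. The check sets the rules side by side.

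**1. Prophylaxis.** Take a patient negative for HBV-DNA and HBsAg and positive for HBc Ab, which indicates past infection.

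| Source | Instruction |
|---|---|
| 3.2.5j | Lamivudine (past infection is named) |
| Table 3-2 | No prophylaxis; monitor HBV-DNA |
| Table 3.4a, footnote 3 | Not in the group recommended for prophylaxis |
| Table 3-3 | On reactivation, start a first antiviral |

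The last row is informative. Table 3-3 tells sites to add a second antiviral for patients who were HBV-DNA or HBsAg positive at baseline, but to start a first one for antibody-only patients. It therefore assumes that antibody-only patients were not on prophylaxis. Three sources agree, and 3.2.5j is the outlier. The exclusion criteria in 3.2.2 cover cirrhosis, chronic hepatitis and hepatitis C. They do not remove a patient whose only finding is a hepatitis B antibody, so such patients can enroll.

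**2. Life-threatening reactivation that resolves within 28 days.**

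- Table 3-3 footnote: recorded as grade 4.
- Table 3-1, grade 4 row: discontinue RAD001. Hepatitis B is not excepted.
- Table 3-3 body: restart one dose lower. It has no rule by grade.

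This conflict does not depend on how the days are counted.

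**3. Length of the hold.** Let d be the interruption in whole days, and assume the 28 days in Table 3-3 run from the start of the hold. The protocol does not say when they start.

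- Table 3-1 discontinues if d ≥ 3 × 7 = 21.
- Section 3.2.4 discontinues if d > 21.
- Table 3-3 restarts if d ≤ 28.

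Table 3-3 therefore disagrees with Table 3-1 for d = 21 to 28, and with 3.2.4 for d = 22 to 28. Because the starting point is unstated, these limits are approximate.

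**4. Ordinary (grade 3) reactivation.** The grade 3 row of Table 3-1 waits for recovery to grade 1 or below and then restarts at the lower dose level. Table 3-3 waits for HBV-DNA to return to its baseline level or below, and allows the same dose if the patient is already on the lowest. Both the recovery criterion and the restart dose differ, so an exception is needed in this row too.

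**5. Lesser points.** For patients on prophylaxis, Table 3-2 tests HBV-DNA about every 6 weeks and footnote 3 every 28 days. Over 24 weeks (168 days) that is 168/42 = 4 tests against 168/28 = 6. The Table 3-3 footnote dates reactivation by HBV-DNA and ALT together, but the table's definition uses HBV-DNA alone.

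**The case against.** The strongest reply is that a specific rule overrides a general one. Section 3.2.5 introduces Table 3-1 as general recommendations, and footnote 3 of Table 3.4a makes Table 3-3 mandatory once reactivation is confirmed. This carries real weight for the 21- versus 28-day question, and 28 days is the better reading. It does not settle the matter: 3.2.4 is also mandatory, stands apart from Table 3-1, and states no exception or order of precedence. Where the authors wanted exceptions to Table 3-1 they wrote them, for pneumonitis and hyperlipidemia. For grade 4, Table 3-3 is silent, so a reader cannot tell whether a restart was intended.

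On prophylaxis, one can say that 3.2.5j leads the reader to 3.2.6.4 and so to Table 3-2. But that pointer concerns management of reactivation, not the choice of who receives lamivudine.

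Three stronger readings are tempting and should not be drawn.

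- A reader might infer that vaccinated patients would be given lamivudine, because "If the patient has a positive Hepatitis B test result, they should be treated with Hepatitis B anti-viral lamivudine 100 mg" taken alone covers vaccine-induced HBs Ab. The preceding sentence limits prophylaxis to past or active infection, 3.2.5j requires a hepatitis history, and Table 3-2 has a column for HBs Ab "with prior HBV vaccination" that ends in "No specific action".
- A reader might infer from the Table 3.4a cell that antibody-only patients get no follow-up HBV-DNA test. The row's own footnote 3 requires one, and section 3.4.1.4.1 sends follow-up testing to both Table 3.4a and section 3.2.6.
- A reader might treat the differing test intervals as a hazard for patients on prophylaxis. Testing every 4 weeks more than meets a schedule of about every 6 weeks, so this is untidy and not harmful.

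**Conclusion.** The point holds as an internal inconsistency in current operative text. The prophylaxis contradiction for past infection is direct, and 3.2.5j is the text that is out of line. The grade 4 contradiction between Tables 3-1 and 3-3 is also direct. The hold-length conflict is softer. It covers holds of about 21 to 28 days (22 to 28 against 3.2.4), assumes that the 28 days start with the hold, and is partly answered by footnote 3.

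The number of patients affected cannot be computed, because the protocol gives no hepatitis B prevalence. It is probably small: 50 patients are planned, and 3.2.5j describes reactivation as sporadic. No efficacy endpoint uses reactivation, and the stated alpha, power and sample size do not depend on it. The protocol should be corrected for patient safety and uniform conduct across sites.

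**What to change.** (a) Replace the first two prophylaxis sentences of 3.2.5j with: *Patients positive for HBV-DNA or HBsAg should receive lamivudine 100 mg, starting 1-2 weeks before RAD001 and continuing for at least 4 weeks after the last dose. Patients negative for both but positive for HBc Ab, or for HBs Ab without prior vaccination, receive no prophylaxis and are monitored as in Table 3-2.* If the clinical team prefers prophylaxis for past infection, change Table 3-2, Table 3-3 and footnote 3 of Table 3.4a instead.

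(b) Add *except hepatitis B reactivation, see Table 3-3* to the grade 3 non-hematological row and the three-week row of Table 3-1, and to the 21-day sentence of 3.2.4.

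(c) Add *Grade 4 reactivation: discontinue RAD001* to Table 3-3. This matches Table 3-1, but it is a clinical choice and the clinical team should confirm it.

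Optional tidying: give one HBV-DNA testing interval per patient group in Table 3-2 and footnote 3 (every 4 weeks fits the visit schedule), and remove the undefined ALT criterion from the Table 3-3 footnote.

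The cost is a wording amendment, with the IRB approval that section 4 requires, and a memo to sites. Nothing in the statistical section changes.

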3.2.6 Management of Side Effects of RAD001

3.2.6.1 Management of stomatitis/oral mucositis/mouth ulcers

Stomatitis/oral mucositis/mouth ulcers due to RAD001 should be treated using local supportive care.

When described, the disorder has been identified as inflammation or ulcers in the mouth. If exam reveals mouth ulcers, rather than a more general inflammation of the mouth, please classify the adverse event as 'mouth ulcers'. If inflammation is limited to the mouth without ulcers please use the term 'stomatitis' rather than the less specific term 'mucositis'.

If the disorder is elsewhere than the mouth please describe the location as well as any specific procedures carried out for exploration (e.g. endoscopy).

Please use the Grading according to the NIH-NCI Common Terminology Criteria for Adverse Events, Version 3.0 (CTCAEv3.0; <http://ctep.cancer.gov/forms/CTCAEv3.pdf>).

- Grade 1: minimal symptoms; normal diet
- Grade 2: symptomatic but can eat -and swallow modified diet
- Grade 3: symptomatic and unable to adequately aliment or hydrate orally
- Grade 4: symptoms associated with life-threatening consequences

Recommendations

For mild toxicity (Grade 1), use conservative measures such as non-alcoholic mouth wash, decadron mouthrinse, or salt water (0.9%) mouth wash several times a day until resolution. For more severe toxicity (Grade 2 or 3), the suggested treatments are topical analgesic mouth treatments (i.e., local anesthetics such as benzocaine, butyl aminobenzoate, tetracaine hydrochloride, menthol, or phenol) with or without topical corticosteroids, such as triamcinolone oral paste 0.1% (e.g. Kenalog in Orabase[®]).

Agents containing hydrogen peroxide, iodine, and thyme derivatives may tend to worsen mouth ulcers. It is preferable to avoid these agents.

Antifungal agents must be avoided unless a fungal infection is diagnosed. In particular, systemic imidazole antifungal agents (ketoconazole, fluconazole, itraconazole, etc.) should be avoided in all patients due to their strong inhibition of RAD001 metabolism, therefore leading to higher RAD001 exposures. Therefore, topical antifungal agents are preferred if an infection is diagnosed. Similarly, antiviral agents such as acyclovir should be avoided unless a viral infection is diagnosed.

3.2.6.2 Management of hyperlipidemia and hyperglycemia

Treatment of hyperlipidemia should take into account the pre-treatment status and dietary habits. Blood tests to monitor hyperlipidemia must be taken in the fasting state. Grade 2 or higher hypercholesterolemia (>300 mg/dL or 7.75 mmol/L) or grade 2 or higher hypertriglyceridemia (>2.5 x upper normal limit) should be treated with a statin or appropriate lipid-lowering medication, in addition to diet. Patients should be monitored clinically and through serum biochemistry for the development of rhabdomyolysis and other adverse events as required in the product label/data sheets for HMG-CoA reductase inhibitors.

Note: Concomitant therapy with fibrates and an HMG-CoA reductase inhibitor is associated with an increased risk of a rare but serious skeletal muscle toxicity manifested by rhabdomyolysis, markedly elevated creatine kinase (CPK) levels and myoglobinuria, acute renal failure and sometimes death. The risk versus benefit of using this therapy should be determined for individual patients based on their risk of cardiovascular complications of hyperlipidemia.

Grade 3 hyperglycemia has been observed in patients receiving RAD001 therapy. In many cases in [Study RAD001C2222] the affected patients had an abnormal fasting glucose at baseline. Based on this finding, it is recommended that optimal glucose control is achieved before starting a patient on RAD001. Study patients should have their glucose levels monitored during RAD001 therapy.

3.2.6.3 Management of non-infectious pneumonitis

Both asymptomatic radiological changes (grade 1) and symptomatic non-infectious pneumonitis (grade 2 = not interfering with activities of daily living or grade 3 = interfering with activities of daily living and oxygen indicated) have been noted in patients receiving RAD001 therapy. Non-infectious pneumonitis has been associated with RAD001 and other mTOR inhibitors (Atkins 2004). In order to monitor for asymptomatic (grade 1) pulmonary

infiltrates, a chest X-ray is required if a CT scan of chest is not used for bi-monthly disease evaluations. Additional chest CT scans may be performed, when clinically necessary. If non-infectious pneumonitis develops, a consultation with a pulmonologist should be considered. If the patient develops grade 3 pneumonitis, treatment with RAD001 should be interrupted and the patient should be treated as medically indicated (short course corticosteroids, oxygen, etc).

Management of non-infectious pneumonitis suspected to be associated with RAD001 and dose modifications instructions are provided in Table 3-2a and Table 3-0, respectively.

Table 3-2a Management of non-infectious pneumonitis

Worst Grade Pneumonitis	Required Investigations	Management of Pneumonitis	RAD001 Dose Adjustment
Grade 1	CT scans with lung windows and pulmonary function testing including: spirometry, DLCO, and room air O₂ saturation at rest. Repeat chest x-ray/CT scan every 2 Cycles until return to baseline.	No specific therapy is required	Administer 100% of RAD001 dose.
Grade 2	CT scan with lung windows and pulmonary function testing including: spirometry, DLCO, and room air O₂ saturation at rest. Repeat each subsequent Cycle until return to baseline**. Consider bronchoscopy *	Symptomatic only. Prescribe corticosteroids if cough is troublesome.	Reduce RAD001 dose until recovery to ≤ Grade 1. RAD001 may also be interrupted if symptoms are troublesome. Patients will be withdrawn from the study if they fail to recover to ≤ Grade 1 within 3 weeks.
Grade 3	CT scan with lung windows and pulmonary function testing including: spirometry, DLCO, and room air O₂ saturation at rest.; Repeat each subsequent Cycle until return to baseline**. Bronchoscopy is recommended *	Prescribe corticosteroids if infective origin is ruled out. Taper as medically indicated.	Hold treatment until recovery to ≤ Grade 1. May restart protocol treatment within 3 weeks at a reduced dose (by one level) if evidence of clinical benefit. Patients will be withdrawn from the study if they fail to recover to ≤ Grade 1 within 3 weeks.
Grade 4	CT scan with lung windows and required pulmonary function testing includes: spirometry, DLCO, and room air O₂ saturation at rest. Repeat each subsequent Cycle until return to baseline**. Bronchoscopy is recommended *.	Prescribe corticosteroids if infective origin is ruled out. Taper as medically indicated.	Discontinue treatment.

*A bronchoscopy with biopsy and/or bronchoalveolar lavage is recommended.

** Pulmonary function tests are dependent on a variety of parameter such as patient's age, gender, height etc. Normal references are provided when a patient undergoes PFT testing based on his or her individual characteristics. These are usually based on normal values published by John L. Hankinson, Robert O. Crapo and Robert L. Jensen et al CHEST November 2003 vol. 124 no. 5 1805-1811.

3.2.6.4 Management of Hepatitis B or C Reactivation

Monitoring and prophylactic treatment for hepatitis B reactivation

Table 3-2 provides details of monitoring and prophylactic therapy according to the baseline results of viral load and serologic markers testing.

Table 3-2 Action to be taken for positive baseline hepatitis B results

Test	Result	Result	Result	Result	Result
HBV-DNA	+	+ or -	-	-	-
HBsAg	+ or -	+	-	-	-
HBs Ab	+ or -	+ or -	+	+ or -	- or + with prior HBV vaccination
HBc Ab	+ or -	+ or -	+ or -	+	-
Recommendation	Prophylaxis treatment should be started 1-2 weeks prior to first dose of study drug Monitor HBV-DNA approximately every 6 weeks		No prophylaxis Monitor HBV-DNA approximately every 3 weeks		No specific action

Antiviral prophylaxis therapy should continue for at least 4 weeks after last dose of study drug. For patients who have already received study drug prior to the approval of the amendment, the same process should be followed at the patient's next visit. The first HBV-DNA result would be regarded as baseline. For hepatitis B reactivation, definition and management guidelines, see Table 3-3 Guidelines for management of hepatitis B.

Table 3-3 Guidelines for management of hepatitis B

HBV reactivation (with or without clinical signs and symptoms)*	
For patients with baseline results: Positive HBV-DNA OR positive HBsAg ----- reactivation is defined as: [Increase of 1 log in HBV-DNA relative to baseline HBV-DNA value OR new appearance of measurable HBV-DNA]	Treat: Start a second antiviral AND Interrupt study drug administration until resolution: ≤ baseline HBV-DNA levels If resolution occurs within ≤ 28 days, study drug should be re-started at one dose lower, if available. If the patient is already receiving the lowest dose of study drug according to the protocol, the patient should restart at the same dose after resolution. Both antiviral therapies should continue at least 4 weeks after last dose of study drug. If resolution occurs > 28 days, patients should discontinue study drug but continue both antiviral therapies at least 4 weeks after last dose of study drug.
For patients with baseline results: Negative HBV-DNA and HBsAg AND [Positive HBs Ab (with no prior history of vaccination)	Treat : Start first antiviral medication AND Interrupt study drug administration until resolution: ≤ baseline HBV-DNA levels If resolution occurs within ≤ 28 days study drug should be re-started at one dose lower, if available. If the patient is already receiving the lowest dose of

against HBV), OR positive HBc Ab]	study drug according to the protocol, the patient should restart at the same dose after resolution. Antiviral therapy should continue at least 4 weeks after last dose of study drug.
reactivation is defined as:	If resolution occurs > 28 days, patients should discontinue study drug but continue antiviral therapy at least 4 weeks after last dose of study drug.
New appearance of measurable HBV-DNA	

* All reactivations of hepatitis B are to be recorded as grade 3 (CTCAE v 3.0 Metabolic Laboratory/Other: Viral Re-activation), unless considered life threatening by the investigator; in which case they should be recorded as grade 4 (CTCAE v 3.0 Metabolic Laboratory/Other: Viral Re-activation). Date of viral reactivation is the date on which **both** DNA and ALT criteria were met (e.g. for a patient who was HBV-DNA positive on 01-JAN-10 and whose ALT reached $\geq 5 \times$ ULN on 01-APR-10, the date of viral reactivation is 01-APR-10).

Screening for Hepatitis C

Patients with a positive Hepatitis C test or known to have a history of HCV infection including those with a negative viral load test at baseline are excluded from the study.

All interruptions or changes to study drug administration must be recorded.

It will be documented whether or not each patient completed the clinical study. If for any patient either study treatment or observations were discontinued the reason will be recorded.

Reasons that a patient may discontinue participation in a clinical study are considered to constitute one of the following:

- adverse event(s)
- abnormal laboratory value(s)
- abnormal test procedure result(s)
- disease progression
- protocol violation
- subject withdrew consent
- lost to follow-up
- administrative problems
- death

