3.2.5g Discrete, reversible changes in liver enzymes have been found to occur in numerous patients during treatment with RAD001 in oncology clinical studies, and in a study in rheumatoid arthritis. In oncology studies, these changes may be evident only in patients without severe underlying morbidity. The increase in transaminase's (AST and ALT) generally appears after 4 weeks of treatment. In all but a few cases it does not exceed Grade 1 ($\leq 2.5 \times \text{ULN}$). Similarly, mild increases in alkaline phosphatases can coexist. Spontaneous corrections or intermittent correction with continued treatment can occur. Serum bilirubin is not increased. In studies of patients with advanced cancers, clinically relevant changes in liver enzymes have been invariably associated with the presence of liver metastases and/or progression of the underlying cancer.

3.2.5h Renal failure has been reported in five suspected cases to date. One patient with no alternative explanation made a complete recovery following study drug adjustment and no treatment/therapy for the event. The rest of the patients had concurrent morbidities, which might have contributed to the reported events.

3.2.5i Hypophosphatemia, hypomagnesemia, hyponatremia and hypocalcemia have been reported as serious adverse reactions. Electrolytes should be monitored in patients treated with RAD001.

Table 3-1 provides general recommendations for the management of patients, with suspected drug toxicities while on treatment with RAD001 as single-agent therapy.

More detailed information regarding RAD001 reported suspected toxicities and individual cases is provided in the [Investigator's Brochure].

3.2.5j Reactivation of Hepatitis B (HBV) has been observed in sporadic cases with patients in this setting with everolimus. Use of antivirals during anti-cancer therapy has been shown to reduce the risk of Hepatitis B virus reactivation and associated morbidity and mortality. A detailed assessment of Hepatitis B/C medical history and risk factors must be done for all patients at screening, with testing performed prior to the first dose of everolimus.

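### For patients already on RAD001 when hepatitis B testing was added, an on-drug HBV-DNA value serves as baseline, so a rise before that first test is not classed as reactivation

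*Combined protocol and SAP*

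**What the plan says.** Section 3.2.5j acknowledges sporadic hepatitis B reactivation under everolimus and asks for a hepatitis assessment of every patient at screening, "with testing performed prior to the first dose of everolimus". For patients dosed before the amendment, section 3.2.6.4 instead provides that "the same process should be followed at the patient's next visit", and adds: "The first HBV-DNA result would be regarded as baseline".

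Table 3-2 sorts patients by baseline result. Those positive for HBV-DNA or HBsAg get antiviral prophylaxis and repeat testing: "Prophylaxis treatment should be started 1-2 weeks prior to first dose of study drug" and "Monitor HBV-DNA approximately every 6 weeks". Those positive only for antibodies get no prophylaxis and are tested about every 3 weeks.

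Table 3-3 defines reactivation against that same baseline. In the first group it is "Increase of 1 log in HBV-DNA relative to baseline HBV-DNA value OR new appearance of measurable HBV-DNA". In the antibody-only group it is "New appearance of measurable HBV-DNA". In both groups the response is to start an antiviral (a second one in the first group, a first one in the other) together with "Interrupt study drug administration until resolution: ≤ baseline HBV-DNA levels". Whether resolution comes within 28 days decides between restarting and discontinuing RAD001. The footnote to Table 3-3 has every reactivation recorded at grade 3, or at grade 4 where the investigator judges it life-threatening.

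**The concern.** A baseline is meant to precede exposure. Here it is drawn after exposure to the drug whose effect on the virus it is supposed to reveal. If HBV-DNA rose between the first dose and the first test, the raised value becomes the reference, and the change that defines reactivation has already dropped out of the comparison.

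The classification has consequences. Footnote 3 of Table 3.4a links interruption or discontinuation to confirmed reactivation under Table 3-3, and the Table 3-3 footnote links the grade 3 or 4 record to it. Grade in turn feeds IRB reporting (section 3.4.5), and reported adverse events feed review by the monitoring committee (section 6.1.1). Two patients with the same viral course can therefore have different entries in the safety record, and a different instruction on study drug, solely because one was dosed before the amendment.

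**Working it through.** The plan states no figure on this point, so there is none to reproduce. The check applies the Table 3-3 definitions to the same viral course twice: once with a true pre-dose value as baseline, once with the first on-drug value.

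Inputs from section 3.2.6.4: reactivation is a rise of at least 1 log over a measurable baseline, or measurable HBV-DNA where none was measurable at baseline; resolution is a return to baseline or below. Assumed: the log10 HBV-DNA levels, which are illustrative only, and HBsAg negative.

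For a measurable baseline B, the trigger is B + 1 and the resolution threshold is B. For an unmeasurable baseline, any measurable value is the trigger.

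| Pre-dose | First on-drug test | Judged against pre-dose value | Judged against first on-drug value | Next trigger under the written rule | Resolution threshold under the written rule |
|---|---|---|---|---|---|
| unmeasurable | 3 log | reactivation (new HBV-DNA) | not reactivation | 3 + 1 = 4 log | 3 log |
| unmeasurable | 5 log | reactivation (new HBV-DNA) | not reactivation | 5 + 1 = 6 log | 5 log |
| 3 log | 5 log | reactivation (5 − 3 = 2, at least 1) | not reactivation (5 − 5 = 0) | 6 log, against 3 + 1 = 4 from the pre-dose value | 5 log, against 3 from the pre-dose value |
| unmeasurable | unmeasurable | no reactivation | no reactivation | any measurable value | unmeasurable |

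Following the 5 log rows forward:

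- If later values stay at 5 log or below, the patient is never classed as having reactivated.
- If a later value reaches 6 log, reactivation is recognised, but with that later date and with 5 log as the level to return to.
- In the last row, a later measurable value is caught normally. The gap is confined to rises completed before the first test.

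The error is not strictly one-way. A patient at 3 log before dosing, unmeasurable at the first on-drug test and back at 3 log later would be called a reactivation under the written rule but not against the pre-dose value.

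On the route taken at the first test, a measurable result places the patient in the first group of Table 3-2, so prophylaxis and monitoring apply. The prophylaxis timing there is tied to a date before the first dose, which has already passed for these patients. No text says how to flag a positive first on-drug result.

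**The case against.** The strongest reply is that this is a transitional provision using the only HBV-DNA value the documents describe for these patients. Drug time before the first test has no HBV-DNA data under any wording. That is true. It is also why the baseline should be recorded as unknown, since calling an on-drug value baseline hides the uncertainty.

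Several safeguards remain and should be credited:

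- The virus is seen at that visit. Table 3-2 and section 3.2.5j both call for an antiviral, and footnote 3 of Table 3.4a has patients on prophylaxis tested every 28 days.
- ALT and AST are in the chemistry panel every 4 weeks, and Table 3-1 acts on grade 3 and 4 toxicity whatever the hepatitis B baseline.
- Under section 3.4.3.1, an abnormal test that needs therapy is an adverse event. The same section counts conditions present before study drug only if they worsen, and a baseline label invites that reading.
- The Table 3-3 footnote dates reactivation to when DNA and ALT criteria are both met, and its example is a patient already HBV-DNA positive whose ALT rises later. On that text such a patient might still be recorded. The definitions in the table contain no ALT criterion, so the point is unresolved.

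A reader might infer that these reactivations go undetected, untreated and uncounted, or that the two groups of patients receive opposite actions. The safeguards above do not support that. An antiviral is called for on either route. What differs is the drug interruption, the reactivation grade and the resolution reference.

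A reader might also infer a biased pooled reactivation rate. Section 7.1 plans no such analysis, and reactivation is not an endpoint.

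**Conclusion.** The point holds in a limited form. For patients dosed before the amendment, a rise in HBV-DNA that occurred on RAD001 before the first test is not classed as reactivation at that test. The Table 3-3 interruption and the grade 3 or 4 reactivation record do not follow, and any later reactivation is dated and resolved against the raised level.

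The conclusion rests on reading Table 3-3 by its HBV-DNA definitions. The levels of 3, 5 and 6 log only show how the rule behaves. The documents do not give the number of patients affected. It may be zero in a trial of at most 50, and the January 2014 summary of changes lists no hepatitis item, so the transitional visit may already be past. No size can be put on any undercount. The effect is on safety classification; the 6-month PFS decision uses no hepatitis B data.

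**What to change.** In the safety data, flag every first HBV-DNA result obtained after RAD001 has started as *on treatment, pre-dose baseline unknown*. Report a detectable one, where there is no prior positive record, as *possible reactivation, timing unknown*. Where routine care has left a pre-dose result, use it. List patients with and without a pre-dose test separately.

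The sponsor should also reconcile four sets of passages. No clinical rule is proposed here.

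- The baseline sentence in section 3.2.6.4 with the reactivation and resolution definitions in Table 3-3.
- The Table 3-2 prophylaxis timing with patients who are already on drug.
- The 6-weekly and 3-weekly monitoring in Table 3-2 with the 28-day testing in footnote 3 of Table 3.4a.
- The HBV-DNA-only definitions in Table 3-3 with its footnote dating reactivation by DNA and ALT together.

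The reporting change costs a clarifying sentence, one derived flag and a split listing. The drawback is that some viraemia present before dosing will be listed as possible reactivation, but it will be labelled as such.
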